### **8.7.3. Subjects Receiving Rescue Medications for HCV**

Subjects that relapse or fail to achieve SVR and begin non-IP HCV treatment will have failure imputed to timepoints that are subsequent to beginning their non-IP HCV treatment regimen regardless of the observed result HCV viral load results. Imputed timepoints should be excluded from quantitative viral load analyses.

The list of rescue medications is presented in Appendix 2.

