### 3. STUDY DESIGN

#### 3.1. General Study Design

This is an open-label trial to evaluate 8 weeks of treatment with BEM + RZR in subjects with chronic HCV infection (Figure 2). Approximately 280 treatment-naïve subjects with genotype (GT) 1, 2, 3, 4, 5, 6, or 7, either without cirrhosis or with compensated cirrhosis, will be enrolled.

A lead-in group of 60 non-cirrhotic subjects will initially be enrolled. At 4 weeks posttreatment, this lead-in group will be evaluated for safety, SVR4, and virologic relapse; enrollment will open to the remaining 220 subjects provided that **CCI** [REDACTED] in the lead-in group experience virologic failure that was not due to poor compliance and no study stopping rules are met (Section 5.6.3).

**Figure 2:** Study Design

a Can be extended to 6 weeks under extenuating circumstances with Sponsor approval.  
BEM = bemnifosbuvir; RZR = ruzasvir; SVR4 = sustained virologic response at 4 weeks posttreatment

Subjects will be screened for up to 4 weeks, although this can be extended for up to 6 weeks for extenuating circumstances with Sponsor approval. Such circumstances may include awaiting reporting of laboratory results or scheduling assessment of cirrhosis (eg, FibroScan®) if needed. Re-screens may be approved on a case-by-case basis by the Sponsor (re-screened subjects will be assigned a new subject number).

At the end of the screening period (Baseline; Day 1), eligible subjects will enter the treatment period and receive BEM + RZR for 8 weeks. After Day 1 during the treatment period, subjects

may self-administer study drugs (ie, IMP) at home, with the exception of subjects who agree to additional PK and/or PK-VK blood sampling as part of up to two substudies. These subjects will be required to take their study drug in the clinic on certain days (see [Table 3](#)).

Subjects will return to the clinic for evaluations at Weeks 1, 2, 4, 6, and 8 (End of Treatment [EOT]) during the treatment period.

Following their last visit of the treatment period (including subjects who prematurely discontinue treatment) subjects will enter the Follow-up period and return to the clinic for evaluations at Follow-up Weeks 4, 12, and 24. End-of-Study (EOS) is defined as the visit at 24 weeks posttreatment.

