Adverse events and concomitant medications will be reviewed during visits throughout the treatment and follow-up periods. Subjects may also be contacted between visits to assess their compliance with the dosing regimen (during the treatment period) and to discuss AEs and concomitant medications.

The primary endpoint is SVR12. Secondary endpoints include virologic failure and SVR24. Exploratory endpoints are resistance to either study drug (BEM or RZR), SVR12 in subgroups defined by demographics and/or baseline characteristics, HCV RNA changes from baseline and exposure-response relationships. Safety endpoints are the incidence of AEs, SAEs, and AEs resulting in treatment discontinuation; clinical laboratory abnormalities; vital sign measurements; and ECG parameters.

At clinical sites that agree to participate, there will be two optional substudies (PK only; PK-VK), each requiring separate consent; up to 100 subjects can consent to either or both. Subjects who consent to the PK-only substudy will provide additional blood samples at any planned treatment visit as early as Week 2 based on convenience for subject and investigator. Subjects who consent to the PK-VK substudy will provide additional blood samples a) on Day 1; and b) on Days 2 and 3 (24 and 48 hours after the first dose;  $\pm$  2 hours). Study drug will be administered at the clinic on these days (see [Table 3](#)).

Patients with HCV or HCV patient groups were not consulted. The study conforms to many aspects of canonical HCV study design and patient care, as described in both health authority guidance  and clinical practice guidelines .

This is a global clinical trial that complies with the European Union Clinical Trial Regulations. Results will be released to a publicly accessible web site (eg, Clinical Trial Information System [CTIS]) after the last European subject's completion of the study. However, if the study is ongoing outside the EU as of that date, results will be released after the last subject's completion date.

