### **5.8.2. Concomitant Medication**

Concomitant therapy consists of any medication (eg, prescription drugs, over the counter drugs, vaccines, herbal or homeopathic remedies, nutritional supplements) used by a subject in addition to study drug treatment. All such medications should be reported to the investigator and recorded on the Concomitant Medications electronic Case Report Form (eCRF). Concomitant medications should be used according to their label.

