**Table 2: Schedule of Assessments**

Study Week/Day:	Screening a	Baseline	Treatment Period					Follow-up Period		
			± 1 day		± 3 days		+ 3 days	Following Last Treatment Visit; ± 5 days	Week 4	Week 12
			Week 1 Day 8	Week 2 Day 15	Week 4 Day 29	Week 6 Day 43	Week 8 Day 57 c			
Eligibility										
Informed consent	X									
Medical history	X									
Demographics	X									
Inclusion/Exclusion Criteria	X	X								
Physical Examination and Vital Signs										
Complete physical examination	X	X					X	X		
Symptom-targeted examination			X	X	X	X			X	
Vital signs	X	X	X	X	X	X	X	X		
Height (screen only) and weight	X	X			X		X	X		
Triplicate 12-lead ECG d	X	X			X		X	X	X	
Liver staging	X									
Laboratory										
Clinical labs and urinalysis	X	X	X	X	X	X	X	X		
HBV (HBsAg), HCV (anti-HCV Ab), and HIV screen; hemoglobin A 1c	X									
Pregnancy test e	X	X			X	X	X	X		
Pharmacodynamics and Pharmacokinetics										
HCV genotyping	X									
HCV RNA quantitation	X	X	X	X	X	X	X	X	X	X
Viral resistance sample f	X	X	X	X	X	X	X	X	X	X

Study Week/Day:	Screening a	Baseline	Treatment Period						Follow-up Period		
			± 1 day		± 3 days		+ 3 days	ET	Following Last Treatment Visit; ± 5 days		
			Week 1 Day 8	Week 2 Day 15	Week 4 Day 29	Week 6 Day 43			Week 4	Week 12	Week 24
PK Sample g		X	X	X	X	X	X				
Optional PK-only substudy h				Serial blood sampling at any treatment period visit as early as Week 2							
Optional PK/VK substudy h			Days 1, 2, and 3								
Study Intervention											
Study drug administration		X	At-home dosing for full treatment period (Days 1-56) unless otherwise specified								
Review compliance with study drugs i			X	X	X	X	X	X			
Adverse Event and Concomitant Medication Monitoring											
Concomitant medications i	X	X	X	X	X	X	X	X	X		
AEs i	X	X	X	X	X	X	X	X	X		
SAEs i	X	X	X	X	X	X	X	X	X	X	X

AEs = adverse events; anti-HCV Ab = anti-HCV antibody; APRI = aspartate aminotransferase (AST) to platelet ratio index; BMI = body mass index; ECG(s) = electrocardiogram(s); ET = early termination; HBsAg = Hepatitis B virus surface antigen; HBV = Hepatitis B virus; HCV = Hepatitis C virus; HIV = Human Immunodeficiency virus; PK = pharmacokinetic; SAEs = serious adverse events; VK = viral kinetics

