a Screening window may be extended to 42 days for extenuating circumstances with Sponsor approval.

b Day 1 assessments performed prior to dosing.

c The last dose is on Day 56. The last visit of the treatment period shall occur no sooner than Day 57 and no later than Day 60 (inclusive).

d Three consecutive determinations collected, with no less than 1 minute between individual ECGs. Complete ECGs prior to any blood draws.

e For females of childbearing potential, serum or urine is acceptable.

f Plasma samples collected for resistance testing. At least one baseline resistance sample is needed (Screening and/or Day 1 predose); there is no protocol deviation if there is one evaluable baseline sample for resistance testing. In addition, the resistance sample is not required for screening and eligibility purposes.

g On Day 1, the PK sample will be obtained predose. The sampling time and time of last dose must be recorded.

h See Table 3

i Subjects may be contacted between visits to assess compliance, concomitant medications, and AEs/SAEs.

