#### 8.7.4. Primary Efficacy Analysis

The primary efficacy endpoint is the proportion of subjects in the PK and Pill compliant per-protocol population (PK/PC-PP) achieving sustained virologic response at 12 weeks post-treatment (SVR12). Table 5 will be used to derive SVR12 in the analysis populations.

**Table 5. Determination of primary outcome (SVR12) for subjects who meet all I/E criteria, did not receive prohibited medications and otherwise met population definition criteria.**

On-Treatment Experience	Has	Has	EOT or	Qualifying Result	Primary Outcome
	12W Post RNA	24W Post RNA	W4 Post HCV Positive		
Met Population Specific Criteria	Y			12W Post	12W Post Result
	N	Y		24W Post	24W Post Result
	N	N	Y	Last value	Failure
	N	N	N	NONE	Excluded from population
Early DC for Drug-Related AE	Y				12W Post Result
	N	Y			24W Post Result
	N	N	Y		Failure
	N	N	N		Failure
Early DC for Virologic Failure			Y		Failure
Other					Excluded from population

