## **9.4. Concomitant and Other Medications**

Concomitant medications (CM) are medications that are administered during the treatment-emergent period. If the (CM) onset date and/or end date is missing or partial, the conventions described in Section 6.8.2 will be used to determine if the medication is concomitant. Medications will be presented based on WHODRUG coding.

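### Protocol Table 2 and the protocol text disagree on medication review after Follow-up Week 4, so the rescue-treatment date that SAP 8.7.3 relies on is not secured and SVR24, and less often SVR12, could read too high

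*SAP*

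**What the plan says.** **The rescue rule.** Under SAP 8.7.3, subjects who relapse or fail to achieve SVR and then start HCV treatment outside the study "will have failure imputed to timepoints that are subsequent to beginning their non-IP HCV treatment regimen", whatever their observed viral load. A list of rescue medications is given as Appendix 2. The section does not say which record supplies the start date.

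**The schedule.** In protocol Table 2 the row "Concomitant medications i" is marked from Screening to Follow-up Week 4 and is empty at Follow-up Weeks 12 and 24. The footnote to that row adds only an option: "Subjects may be contacted between visits to assess compliance, concomitant medications, and AEs/SAEs".

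**The text.** Protocol 3.1 says "Adverse events and concomitant medications will be reviewed during visits throughout the treatment and follow-up periods", and the synopsis says the same. Subjects "return to the clinic for evaluations at Follow-up Weeks 4, 12, and 24". Protocol 5.8.2 asks for all such medications to be recorded on the Concomitant Medications eCRF and sets no end date.

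**The derivation.** In SAP 8.7.4, Table 5, a subject with no Week 12 sample but a Week 24 sample receives the "24W Post Result". The column for a positive EOT or post-treatment Week 4 result is blank in that row. SAP 8.7.2.2 defines relapse as RNA at or above LLOQ after treatment in a subject who completed at least 51 days and was below LLOQ at discontinuation.

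**Rescue timing.** Protocol 5.6.1 places the offer of post-study HCV treatment after completion of study-related procedures. SAP 8.7.3 assumes that such treatment can begin before later study timepoints.

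**The concern.** Relapse is found from the Follow-up Week 4 and Week 12 samples. Rescue would mostly begin after those results are known, and so after the last medication review marked in Table 2. A site that works from Table 2 has no scheduled prompt to record it. A site that works from section 3.1 does.

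If the start date is missing, SAP 8.7.3 has nothing to act on, and a virologic failure cured by another regimen looks like a sustained response. Table 5 gives no second line of defence, because an earlier post-treatment positive does not stop the Week 24 result from being used. The supportive analysis in the safety population (SAP 8.7.5) uses the same methods and would carry the same error. The error works in one direction only: it turns failures into responders.

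**Working it through.** **1. Marks in Table 2.** The half of the table that holds these rows has 11 visit columns: Screening, Baseline, Weeks 1, 2, 4, 6 and 8, ET, and Follow-up Weeks 4, 12 and 24.

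| Row | Marks | Last marked visit |
|---|---|---|
| Concomitant medications | 9 | Follow-up Week 4 |
| AEs | 9 | Follow-up Week 4 |
| SAEs | 11 | Follow-up Week 24 |

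Column positions are inferred from the order of marks in extracted text. The AE and SAE rows support the reading: protocol 7.2 ends AE collection 4 weeks after the last dose and carries SAEs to the end of the study.

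**2. What happens to a relapser who is rescued successfully.**

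| Path | Rescue recorded | Rescue not recorded |
|---|---|---|
| (a) Relapse, rescue, Week 24 RNA below LLOQ | SVR24 failure (8.7.3) | SVR24 success |
| (b) Week 4 relapse, rescue before the Week 12 sample, Week 12 RNA below LLOQ | SVR12 failure (8.7.3) | SVR12 success |
| (c) Week 4 relapse, rescue, Week 12 missing, Week 24 RNA below LLOQ | SVR12 failure (8.7.3) | SVR12 success through Table 5 |

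Path (b) is helped by two rules. The Week 12 window runs from EOT+70 to EOT+146 (SAP Table 4), and the latest value in a window is used (SAP 8.7.1). A late on-rescue sample could therefore replace an earlier positive one. Path (c) needs a Week 24 value to exist already, because the primary analysis is run on data through 12 weeks post-treatment (SAP 5.2).

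**3. The plan's own figures.** Expected N: 0.95 × 280 = 266 overall, and 0.95 × 75 = 71.25, taken as 71, in GT3. The lower bounds in SAP Table 3 (protocol Table 5) reproduce with the Wilson score limit

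L = [p + z²/(2n) − z·√(p(1−p)/n + z²/(4n²))] / (1 + z²/n), with z = 1.645 (one-sided 95%).

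- 253/266 = 95.11%: L = 92.45%, stated 92%.
- 255/266 = 95.86%: L = 93.35%, stated 93%.
- 68/71 = 95.77%: L = 89.89%, stated 90%.

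**4. Size of the error.** Each misclassified subject adds 1/266 = 0.38 percentage points overall, or 1/71 = 1.41 points in GT3. The documents give no rate of unrecorded rescue. The number misclassified (k) is an assumption, shown from 0 to 5 overall and 0 to 2 in GT3. The starting failures (13 of 266 and 4 of 71) are also assumed, so that the true rate sits near 95%. Intervals are two-sided 95% Wilson.

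| N | k | Observed SVR | 95% CI |
|---|---|---|---|
| 266 | 0 | 253/266 = 95.11% | 91.82 to 97.12 |
| 266 | 1 | 254/266 = 95.49% | 92.28 to 97.40 |
| 266 | 3 | 256/266 = 96.24% | 93.22 to 97.95 |
| 266 | 5 | 258/266 = 96.99% | 94.18 to 98.47 |
| 71 | 0 | 67/71 = 94.37% | 86.39 to 97.79 |
| 71 | 1 | 68/71 = 95.77% | 88.30 to 98.55 |
| 71 | 2 | 69/71 = 97.18% | 90.30 to 99.22 |

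From the assumed GT3 start, one subject moves the observed rate from below to above the 95% that the sample-size section uses as its reading mark. The one-sided bound moves from 88.03% to 89.89%.

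**The case against.** A reader might infer from Table 2 that rescue treatment after Follow-up Week 4 is not captured at all. The documents do not support that. The synopsis and section 3.1 require medication review at visits throughout follow-up, section 5.8.2 requires recording with no end date, and between-visit contact is allowed. The existence of Appendix 2 suggests that rescue is expected and tracked. The possible reimbursement of post-study medication (protocol 1.4 and 5.6.1) is another way the sponsor might learn of it. Neither the eCRF nor the content of Appendix 2 is visible here.

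SAP 9.4 might also be read as cutting off collection, since it says "Concomitant medications (CM) are medications that are administered during the treatment-emergent period" and that period ends 4 weeks post-treatment (SAP 9.1). But it sits in the safety chapter and defines a display. It does not limit what is collected, and 8.7.3 does not refer to it.

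The SVR12 route through Table 5 is narrow. It needs a Week 4 relapse, effective rescue, a missed Week 12 sample, an available Week 24 value and no record of the rescue, all in one subject. If protocol 5.6.1 is followed literally, rescue before Week 24 should be uncommon. An observed relapse should also still appear under the virologic-failure endpoint. The study is descriptive and has no hypothesis test.

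All of this limits how often the error could occur. It does not remove the contradiction between table and text, supply the missing data source, or close path (a) for SVR24.

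**Conclusion.** The point holds as an internal inconsistency with a one-directional consequence. Table 2 and the protocol text disagree on medication review at Follow-up Weeks 12 and 24, and SAP 8.7.3 depends on information from that interval without naming its source. Capture is not secured; the documents do not show that it is absent.

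The main exposure is SVR24, a secondary endpoint. SVR12 is exposed through a Week 12 sample taken on rescue, and through the Week 24 back-fill when Week 12 is missing. The bias can only be upward, at 0.38 points per subject overall and 1.41 points in GT3. The total rests on an assumed count of unrecorded rescues, so the larger shifts in the table are illustrations and not estimates. Severity: moderate.

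**What to change.** 1. **Protocol Table 2.** Align the concomitant-medication row with the synopsis and section 3.1 by marking Follow-up Weeks 12 and 24, at minimum for non-study HCV treatment with its name and start date.
2. **SAP 8.7.3.** Name that record as the source for the failure imputation, through end of study.
3. **SAP Table 5.** Where Week 12 is missing and Week 24 is present, score Failure if post-treatment relapse under 8.7.2.2 was already documented, or if non-study HCV treatment began before the Week 24 sample. Do not use a positive EOT result alone as a block. Table 5 scores a subject with a Week 12 sample on that result whatever the EOT value, so such a block would make the outcome depend on whether the Week 12 sample was missed.
4. **Rescue timing.** Reconcile protocol 5.6.1 with SAP 8.7.3 on whether non-study HCV treatment can begin before the remaining study timepoints.

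The cost is one question at two visits that already take place, a sentence in 8.7.3, a condition in Table 5 and a wording check on 5.6.1. No new procedure is needed. The reported rate may be slightly less favourable if any such subjects exist.

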#### 8.7.4. Primary Efficacy Analysis

The primary efficacy endpoint is the proportion of subjects in the PK and Pill compliant per-protocol population (PK/PC-PP) achieving sustained virologic response at 12 weeks post-treatment (SVR12). Table 5 will be used to derive SVR12 in the analysis populations.

**Table 5. Determination of primary outcome (SVR12) for subjects who meet all I/E criteria, did not receive prohibited medications and otherwise met population definition criteria.**

On-Treatment Experience	Has	Has	EOT or	Qualifying Result	Primary Outcome
	12W Post RNA	24W Post RNA	W4 Post HCV Positive		
Met Population Specific Criteria	Y			12W Post	12W Post Result
	N	Y		24W Post	24W Post Result
	N	N	Y	Last value	Failure
	N	N	N	NONE	Excluded from population
Early DC for Drug-Related AE	Y				12W Post Result
	N	Y			24W Post Result
	N	N	Y		Failure
	N	N	N		Failure
Early DC for Virologic Failure			Y		Failure
Other					Excluded from population

#### 8.7.5. Sensitivity Analyses of the Primary Efficacy Results

Planned supplemental analyses to support the primary endpoint results include all efficacy analysis for the safety population.

These analyses will be carried out using the same methods as those for the primary efficacy analysis.

### 8.8. Analysis of the Secondary Efficacy Endpoints

Secondary analysis will include:

- The proportion of subjects in the Efficacy Evaluable and Pill Compliant per-protocol populations (EE-PP and PC-PP) achieving sustained virologic response at 12 weeks post-treatment (SVR12). Table 5 will be used to derive SVR12 in the EE-PP and PC-PP populations.

- The proportion of subjects in the EE-PP, PC-PP and PK/PC-PP populations experiencing virologic failure (on treatment or post-treatment relapse), estimated and presented with 95% CIs using the Wilson score method.
- The proportion of subjects in the EE-PP , PC-PP and PK/PC-PP populations achieving SVR24, analyzed using the same method as for SVR12.

Virologic failure is defined as a confirmed 1 log10 increase in HCV RNA from post-baseline nadir, or confirmed increase in HCV RNA  $\geq$  LLOQ in any subject who achieved HCV RNA  $<$  LLOQ.

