##### **3.1.2. Secondary Objectives**

The secondary objectives of this study are:

- To evaluate the efficacy of BEM + RZR, as assessed by the proportion of subjects experiencing virologic failure (either on-treatment or post-treatment relapse [by 12 weeks post-treatment])
- To evaluate the efficacy of BEM + RZR as assessed by the proportion of subjects achieving SVR24

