### **8.7.2. Failure to Achieve Sustained Virologic Response**

Subjects may fail to achieve sustained virologic response if they meet virologic failure criteria or for other non-virologic reasons (such as premature discontinuation of study drug or lost to follow-up).

There are two types of virologic failure: on-treatment virologic failure and post-treatment relapse.

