#### **8.7.2.1. On-Treatment Virologic Failure**

On-treatment virologic failure is defined as any of the following, while on-treatment:

- Not achieving  $\text{HCV RNA} < \text{LLOQ}$
- Confirmed 1  $\log_{10}$  increase in HCV RNA from post-baseline nadir (would call this “virologic rebound” if we want to name it in parenthesis)
- Confirmed increase in  $\text{HCV RNA} \geq \text{LLOQ}$  in any subject who achieved  $\text{HCV RNA} < \text{LLOQ}$

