#### **8.7.2.2. Post-Treatment Relapse**

Post-Treatment Relapse is defined as  $\text{HCV RNA} \geq \text{LLOQ}$  after treatment discontinuation in a subject who completed the treatment regimen (at least 51 days) and who had  $\text{HCV RNA} < \text{LLOQ}$  at the time of treatment discontinuation.

Note: Week 8 HCV RNA should be considered “on-treatment” in any subject who received 51 or more days of treatment.

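### SAP 8.8 defines virologic failure by two confirmed rises only, in conflict with SAP 8.7.2 on non-response, unconfirmed relapse and subjects who stop before 51 days

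*SAP*

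**What the plan says.** SAP 3.1.2 sets the secondary objective as the proportion with "virologic failure (either on-treatment or post-treatment relapse [by 12 weeks post-treatment". Protocol 8.4.2 gives the same 12-week limit.

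SAP 8.7.2 builds the concept from two parts: "There are two types of virologic failure: on-treatment virologic failure and post-treatment relapse".
- **On treatment (8.7.2.1).** Introduced by "On-treatment virologic failure is defined as any of the following, while on-treatment", the list has three criteria: never reaching HCV RNA below LLOQ; a confirmed 1 log10 rise from nadir; a confirmed return to LLOQ or above. The first carries no confirmation requirement.
- **Relapse (8.7.2.2).** This is HCV RNA at or above LLOQ "after treatment discontinuation in a subject who completed the treatment regimen (at least 51 days) and who had" RNA below LLOQ when treatment stopped. No confirmation is asked for.

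SAP 8.8 then specifies the secondary analysis in the EE-PP, PC-PP and PK/PC-PP populations. The bullet estimates the proportion "experiencing virologic failure (on treatment or post-treatment relapse), estimated and presented with 95% CIs using the Wilson score method". The section closes with its own definition: "Virologic failure is defined as a confirmed 1 log 10 increase in HCV RNA from post-baseline nadir", or a confirmed return to LLOQ or above in someone who had been below it. Nothing else qualifies.

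**The concern.** The two criteria in the closing sentence of 8.8 are those of Protocol 5.6.1, which defines on-treatment failure for the purpose of stopping treatment in an individual. Used as the whole definition of the endpoint, they leave out non-response, contain no relapse category, and require every event to be confirmed. That contradicts 8.7.2 and also the bullet in the same section. No text says which prevails.

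At stake are the virologic failure proportion, a secondary endpoint named in the protocol, and the resistance analyses in SAP 8.9 (baseline and emergent NS5A and NS5B variants among failures), whose membership is set by failure status. The trial is open-label, so a choice left until programming could be made with outcomes in view.

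**Working it through.** **Inputs.** Definitions: SAP 8.7.2.1, 8.7.2.2 and 8.8. RNA schedule: Protocol Table 2. Evaluable N: SAP 4.3.1. The documents give no expected number of failures and no expected number of reclassified subjects.

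**Plan's own figure.** 95% of 280 enrolled = 0.95 × 280 = 266, as SAP 4.3.1 states.

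**Classifying the same subject under each text**

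| Subject | SAP 8.7.2 | SAP 8.8, literal |
|---|---|---|
| 1. Never below LLOQ on treatment, no confirmed 1 log10 rise | Failure (on treatment) | Not a failure |
| 2. Never below LLOQ on treatment, later confirmed 1 log10 rise | Failure | Failure |
| 3. At least 51 days, below LLOQ at stopping, one later value at or above LLOQ, no repeat | Failure (relapse) | Not a failure |
| 4. As 3, with a second value at or above LLOQ | Failure | Failure |
| 5. Under 51 days, below LLOQ at stopping, confirmed value at or above LLOQ afterwards | Neither type | Failure |

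The texts agree on rows 2 and 4. They disagree on rows 1, 3 and 5, and not all in the same direction.

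**Can row 3 arise?** Post-treatment RNA is scheduled at Weeks 4, 12 and 24 only, and no repeat after treatment is required. A relapse seen at Week 4 can be confirmed at Week 12. One first seen at Week 12 has no scheduled confirming sample until Week 24, so it depends on an unscheduled sample or on Week 24 data being available at the analysis. SAP 8.7.1 also keeps one RNA result per timepoint, the latest in the window. The SAP does not say how a repeat inside the same window would serve as confirmation.

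**Can row 5 arise?** Yes. EE-PP requires only one dose, with eligibility, medication and RNA conditions. PC-PP and PK/PC-PP admit subjects who stopped early for a drug-related AE.

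**Size, for scale only**
- Shift per reclassified subject: 1/266 = 0.38 percentage points, whatever the number of failures.
- Assumed 13 failures: 13/266 = 4.9%; one subject is 1/13 = 7.7% of failures.
- Assumed range of 8 to 18 failures: 8/266 = 3.0%, one subject being 1/8 = 12.5% of failures; 18/266 = 6.8%, one subject being 1/18 = 5.6%.
- Moving three subjects from 13 (also an assumption): 10/266 = 3.8% or 16/266 = 6.0%.

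**The case against.** The best defence is that the closing sentence of 8.8 is a carry-over from Protocol 5.6.1. The bullet above it names the two categories of 8.7.2, and a programmer would probably follow those. That explains the sentence but does not remove it: it is worded as a definition and sits directly under the endpoint.

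Four further points limit the reach of the finding, and all four stand.
- Unscheduled RNA samples are foreseen (SAP 6.7.4) and the Week 12 window runs to EOT+146. Lead-in subjects will reach Week 24 well before later enrollees reach Week 12. So 8.8 may miss a Week 12 relapse; it does not always do so.
- SAP 8.7.2 does give early stoppers a place, among non-virologic reasons for not achieving SVR. Row 5 is a conflict between two texts, not a gap in 8.7.2.
- The study is single-arm and descriptive, with no tests. SVR12 comes from SAP Table 5, and for subjects with a Week 12 or Week 24 result the 8.8 sentence plays no part in deciding response.
- The illustrative shifts are small against sampling error. The Wilson 95% interval for 13/266 is about 2.9% to 8.2%, which contains both 3.8% and 6.0%.

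A reader might infer that 8.8 also governs the lead-in enrolment decision, where 7/60 = 11.7% closes enrolment and 6/60 = 10.0% does not. The documents do not show this. SAP 5.1 has its own wording (on-treatment failure or relapse by 4 weeks), which follows the categories of 8.7.2 and asks for no confirmation. That one subject can reverse the decision is true of any borderline count.

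A reader might also infer that Week 24 relapses will enter this endpoint, since 8.7.2.2 and 8.8 set no time limit. The objective and Protocol 8.4.2 do set one, and SAP 8.2 describes the Week 24 analysis as SVR24-related efficacy and later safety. What remains is a missing cross-reference.

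**Conclusion.** The closing definition in SAP 8.8 is wrong as written: it conflicts with 8.7.2 and with its own bullet. Followed literally, it can undercount failures by omitting non-responders and unconfirmed relapses, while adding some early stoppers with a confirmed rebound. The conflict rests on the current text alone and needs no assumption. Its size does: 0.38 points per subject follows from the planned 266, but how many subjects would be reclassified is unknown.

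This should be fixed, but it is not critical. It affects a descriptive secondary endpoint and the resistance tables. The documents do not support extending it to the lead-in decision or to the SVR12 rule for subjects with Week 12 or Week 24 results.

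**What to change.** 1. Delete the definition sentence in SAP 8.8 and refer instead to 8.7.2.1 and 8.7.2.2.
2. Carry the limit of 12 weeks post-treatment from SAP 3.1.2 and Protocol 8.4.2 into that bullet, and report later relapses alongside SVR24.
3. Add the same cross-reference to SAP 5.1 with its Week 4 limit, as a clarification only.
4. Keep the 51-day condition of 8.7.2.2. Show subjects who stopped before 51 days while below LLOQ and later had RNA at or above LLOQ as a separate row in the reasons-for-failure table.

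The cost is SAP wording before database lock, with no change to visits, samples or treatment. The reported failure rate may be slightly higher than under a literal reading of 8.8.
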